## ABBREVIATIONS

Abbreviation	Definition
ADR	adverse drug reaction
AE	adverse event
AESI	adverse event of special interest
CFR	Code of Federal Regulations
CI	confidence interval
eCRF	electronic case report form
FDC	fixed-dose combination
GPP	Good Pharmacoepidemiology Practices
HbA1c	glycated hemoglobin
MedDRA	Medical Dictionary for Regulatory Activities
SAE	serious adverse event
T2DM	type 2 diabetes mellitus

## 1. INTRODUCTION

The purpose of this statistical analysis plan (SAP) is to describe the statistical analyses and methods for Protocol Alogliptin-5009 (Version 1.1, released on 1-Apr-2016).

All decisions regarding final analysis, as defined in this SAP document, have been made prior to Database Lock (DBL) of the study data.

## 2. STUDY OBJECTIVE (S)

### 2.1. Primary Objective

The primary objective of this study is to describe the real-world clinical response to treatment with alogliptin or alogliptin FDCs as assessed by glycated hemoglobin (HbA1c) level change in patients who have been diagnosed with T2DM and initiated alogliptin or alogliptin FDCs therapy during the observational period.

### 2.2. Secondary Objective

The secondary objectives of this study are:

- To describe real-world clinical response to treatment with alogliptin or alogliptin FDCs in patients who have been diagnosed with T2DM and initiated alogliptin or alogliptin FDCs therapy during the observational period, as assessed by:
  - Change from baseline in HbA1c level on alogliptin or its FDCs therapy in subgroups with different clinical characteristics;
  - HbA1c levels reduction to the goal of <7.0%;
  - HbA1c reduction >0.3% with no tolerability findings (hypoglycemic event, or weight gain  $\geq 5\%$ );
  - To evaluate fasting blood glucose dynamics in patients with diabetes mellitus type 2 over time (V1-V2-V3);
  - To evaluate the effect of alogliptin or alogliptin FDCs on glycosylated hemoglobin (HbA1c) level dynamics in patients with diabetes mellitus type 2 (V3) in dependence on clinical characteristics;
  - Safety (as assessed by adverse drug reactions [ADRs], serious AEs [SAEs], and AEs of special interest [AESI]) to treatment with alogliptin or alogliptin FDCs in standard clinical practice;

- To describe utilization pattern information of alogliptin and alogliptin FDCs (as assessed by percentage of patients who remain on treatment, and time to alogliptin or alogliptin FDCs dose escalation or dose reduction) during the observation period in patients who have been diagnosed with T2DM and initiated alogliptin or alogliptin FDCs therapy during the observational period.

### 2.3. Exploratory Objective

Company Confidential Information

## 3. STUDY DESIGN

This is an observational, prospective, multicenter study in adult patients with T2DM diagnosis who have made the decision, along with their treating physician, to begin treatment with alogliptin or alogliptin FDCs.

The purpose of this study is to observe alogliptin and alogliptin FDCs utilization patterns, as well as clinical response to treatment with alogliptin or alogliptin FDCs, in standard clinical practice. No investigational product will be administered in this study.

The observational study will include approximate 1142 patients with T2DM treated with alogliptin or alogliptin FDCs in approximately 40 sites.

The planned maximum duration of this study per patient will be 6 months or up to loss to follow-up or death, whichever occurs first. In this study, Patients will attend a baseline visit followed by visits approximately at Month 3 and 6. Patients will not be asked to travel to the site only for the purpose of this study; the study visits will be performed during regular doctor's appointments.

## 4. ENDPOINTS

### 4.1. Primary Endpoint

- The primary endpoint is Change from baseline in HbA1c level on alogliptin or its FDCs therapy (V3).

### 4.2. Secondary Endpoint

The secondary endpoints related to real-world clinical response to alogliptin or alogliptin FDCs are the following:

- Clinical response rates: incidence rates of responders. The following definitions of response will be used as secondary endpoints:
  - Change from baseline in HbA1c level on alogliptin or its FDCs therapy in subgroups with different clinical characteristics (V3).
  - HbA1c levels reduction to the goals of <7.0% (V3).
  - HbA1c reduction >0.3% with no tolerability findings (hypoglycemic event, or weight gain  $\geq 5\%$ ) (V3).
  - To evaluate the effect of alogliptin and its FDCs on fasting blood glucose dynamics in patients with diabetes mellitus type 2 over time (V1-V2-V3).
- To evaluate the effect of alogliptin or alogliptin FDCs on glycosylated hemoglobin (HbA1c) level dynamics in patients with diabetes mellitus type 2 in dependence on clinical characteristics (V1-V2-V3).
- ADRs, SAEs, and AESIs.

The secondary endpoints related to alogliptin or alogliptin FDCs utilization patterns are the following:

- Percentage of patients who remain on treatment with alogliptin or alogliptin FDCs (V2-V3).
- Time to alogliptin or alogliptin FDCs dose escalation or dose reduction (V2-V3).

### 4.3. Exploratory Endpoint

Company Confidential Information

- 
- 
- 
-

- Time to add-on therapy (V2-V3).
- Time to T2DM treatment switching/discontinuation.
- Reasons for alogliptin or alogliptin FDCs discontinuation.
- Number of hospitalizations, emergency room visits, and physician office visit.
- Length of hospital stay.

## 5. STATISTICAL HYPOTHESIS

NA.

## 6. SAMPLE SIZE CONSIDERATION

[figure not shown]
Sample size was calculated for the primary endpoint of the study: to evaluate the effect of Alogliptin or its FDCs on glycosylated hemoglobin (HbA1c) level in patients with diabetes mellitus type 2 (V3). Sample size was calculated using SAS 9.3 proc power procedure (power for Confidence Interval for Paired Mean Difference as for accuracy of parameter estimation) for following parameters (fixed scenario elements):

Fixed Scenario Elements	
Distribution	Normal
Method	Exact
Correlation	0.35
Nominal Prob(Width)	0.9
Number of Sides	2
Alpha	0.05
Prob Type	Conditional

Standard deviation was assessed based on S. Del Prato et al study and was considered to be at most 0.70% (for glycosylated hemoglobin level dynamics). To determine required number of patients values from 0.60% to 0.70% were taken. Desired half-width for parameter estimation was set as range between 0.05 – 0.1. Following required number of pairs were calculated:

Computed N Pairs				
Index	Half-Width	Std Dev	Actual Prob(Width)	N Pairs
1	0.05	0.60	0.904	770
2	0.05	0.65	0.904	899

3	0.05	0.70	0.900	1037
4	0.06	0.60	0.904	542
5	0.06	0.65	0.903	632
6	0.06	0.70	0.903	729
7	0.07	0.60	0.906	404
8	0.07	0.65	0.902	470
9	0.07	0.70	0.904	542
10	0.08	0.60	0.902	313
11	0.08	0.65	0.907	365
12	0.08	0.70	0.905	420
13	0.09	0.60	0.905	251
14	0.09	0.65	0.906	292
15	0.09	0.70	0.907	336
16	0.10	0.60	0.904	206
17	0.10	0.65	0.902	239
18	0.10	0.70	0.904	275

For the worst-case scenario of half-width as 0.05, if Std Dev is 0.65, the required number of pairs is 899. Taking into account a possible dropout of 25%, to reach study objectives in regard to this endpoint, it is recommended to enroll at least 1199. If taking Std Dev as 0.60 or 0.70, the required number of pairs is from 770 or 1037. Taking into account a possible dropout of 25%, it is recommended to enroll at least 1027 or 1383 patients into the study.

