The HbA1c outcomes (change of HbA1c from baseline to different follow-up period, and HbA1c clinical response rates) will be summarized as descriptive statistics and incidence rates. Secondary study outcome - change from baseline in glycosylated hemoglobin level on alogliptin or its FDCs therapy in subgroups with different clinical characteristics, is proposed to use multifactorial regression model to determine factors related to effect of alogliptin or its FDCs.

Overall and center-specific proportion of participants remaining on alogliptin at the end of the follow-up period will be summarized as frequency and percentages. Treatment patterns will be summarized at each follow-up time and overall at 6 months as descriptive statistics and incidence rates. Alternatively, Kaplan-Meier curves may be used. Receipt of another T2DM treatment will be summarized at each time period and overall at 6 months as incidence rates. Similar analyses will be performed for other time to event endpoints.

Other endpoints (rates of comorbidities and complications, changes in body weight, number of hospitalizations and healthcare resources utilization, and length of hospitalization) will be summarized by descriptive statistics and incidence rates at each time period and for the overall duration.

All safety endpoints (ADRs, SAEs, and AESIs) will be summarized.

Date of Protocol:

1st April 2016

List of Abbreviations

Abbreviation	Definition
ADR	adverse drug reaction
AE	adverse event
AESI	adverse event of special interest
CFR	Code of Federal Regulations
CI	confidence interval
CRO	contract research organization
DPP-4	dipeptidyl peptidase-4
eCRF	electronic case report form
FDC	fixed-dose combination
GPP	Good Pharmacoepidemiology Practices
HbA1c	glycated hemoglobin
ICF	informed consent form
IEC	independent ethics committee
IRB	institutional review board
MedDRA	Medical Dictionary for Regulatory Activities
SAE	serious adverse event
T2DM	type 2 diabetes mellitus

1 Introduction

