3.1 Study Design

This is an observational, prospective, multicenter study in adult patients with T2DM diagnosis who have made the decision, along with their treating physician, to begin treatment with alogliptin or alogliptin FDCs.

This is a non-interventional study as defined in the Directive 2001/20/EC (The European Parliament and the Council of the European Union 2001) and will follow the Good Pharmacoepidemiology Practices (GPP) guidelines (Epstein 2005). This means that:

- The assignment of a patient to a particular therapeutic strategy is not decided in advance by the study protocol but falls within current practice.
- No additional diagnostic or monitoring procedures shall be applied to the patients.
- Epidemiological methods shall be used for the analysis of collected data.
- The prescription of alogliptin or alogliptin FDCs is clearly separated from the decision to include the patient in the study.

The purpose of this study is to observe alogliptin and alogliptin FDCs utilization patterns, as well as clinical response to treatment with alogliptin or alogliptin FDCs, in standard clinical practice. No investigational product will be administered in this study.

The observational study will include approximate 1199 patients with T2DM treated with alogliptin or alogliptin FDCs in approximately 40 sites.

The planned maximum duration of this study per patient will be 6 months or up to loss to follow-up or death, whichever occurs first. China Guideline For Type 2 Diabetes recommends HbA1c as the gold standard for blood glucose monitoring. The guideline recommends HbA1c should be tested every 3 months when new treatment regimen is initiated, and when HbA1c is in the treatment target, HbA1c test can be followed every 6 months. In this study, since the treatment of all the patients recruited are with alogliptin initiated, according to the guideline and the standard clinical practice, HbA1c is normally tested every 3 months before HbA1c hits the treatment target and keep stable. So in this study, Patients will attend a baseline visit followed by visits approximately at Month 3 and 6.

Patients will not be asked to travel to the site only for the purpose of this study; the study visits will be performed during regular doctor's appointments.

The data collected for this study are detailed in Section 6, and the Data Collection Schedule is provided in Table 12-1.

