7.5 Sample Size Calculations

[figure not shown]
Sample size was calculated for the primary endpoint of the study: to evaluate the effect of Alogliptin or its FDCs on glycosylated hemoglobin (HbA1c) level in patients with diabetes mellitus type 2 (V3). Sample size was calculated using SAS 9.3 proc power procedure (power for Confidence Interval for Paired Mean Difference as for accuracy of parameter estimation) for following parameters (fixed scenario elements):

Fixed Scenario Elements	
Distribution	Normal
Method	Exact
Correlation	0.35
Nominal Prob(Width)	0.9
Number of Sides	2
Alpha	0.05
Prob Type	Conditional

Standard deviation was assessed based on S. Del Prato et al study and was considered to be at most 0.70% (for glycosylated hemoglobin level dynamics). To determine required number of patients values from 0.60% to 0.70% were taken. Desired half-wide for parameter estimation was set as range between 0.05 – 0.1. Following required number of pairs were calculated:

Computed N Pairs				
Index	Half-Width	Std Dev	Actual Prob(Width)	N Pairs
1	0.05	0.60	0.904	770
2	0.05	0.65	0.904	899
3	0.05	0.70	0.900	1037
4	0.06	0.60	0.904	542
5	0.06	0.65	0.903	632
6	0.06	0.70	0.903	729
7	0.07	0.60	0.906	404
8	0.07	0.65	0.902	470
9	0.07	0.70	0.904	542

10	0.08	0.60	0.902	313
11	0.08	0.65	0.907	365
12	0.08	0.70	0.905	420
13	0.09	0.60	0.905	251
14	0.09	0.65	0.906	292
15	0.09	0.70	0.907	336
16	0.10	0.60	0.904	206
17	0.10	0.65	0.902	239
18	0.10	0.70	0.904	275

For the worst-case scenario of half-width as 0.05, if Std Dev is 0.65, the required number of pairs is 899. Taking into account a possible dropout of 25%, to reach study objectives in regard to this endpoint, it is recommended to enroll at least 1199. If taking Std Dev as 0.60 or 0.70, the required number of pairs is from 770 or 1037. Taking into account a possible dropout of 25%, it is recommended to enroll at least 1027 or 1383 patients into the study.

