9.3 Investigator Documentation

Prior to beginning this observational study, the investigator will be asked to provide the following documents:

- IEC/IRB approval, as required by country-specific regulations, as detailed in Section 8.1

- Authority approval, as required by country-specific regulations
- Original investigator-signed investigator agreement page of the protocol
- Curriculum vitae for the investigator
- Financial disclosure information
- IEC/IRB-approved informed consent and samples of site advertisements for recruitment for this study (if permitted by local regulations)
- Laboratory certifications and normal ranges for any local laboratories used by the site
- Local insurance certificate, if applicable
- Written agreement between Takeda and study site

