### **8.4.2. Secondary Efficacy Analyses**

The secondary HbA1c or fasting blood glucose outcomes (HbA1c clinical response rates) will be summarized by treatment as descriptive statistics and incidence rates.

If multiple HbA1c levels are available, then the assessment closest to the visit time point will be used. Clinical response rates: incidence rates of responders. The following definitions of response will be used: (1) HbA1c level reduction to the goals of <7.0%. (2) HbA1c reduction >0.3% with no tolerability findings (hypoglycemic event, or weight gain  $\geq 5\%$ ).

- HbA1c level change from baseline in subgroups with different clinical characteristics. It is proposed to use multifactorial regression model to determine factors related to effect of alogliptin and its FDCs on HbA1c level dynamics. Change from baseline in HbA1c level on alogliptin or its FDCs therapy (V3) in subgroups with different clinical characteristics will be summarized using relevant descriptive statistics and analyzed using Multiple Linear Regression with following predictors: prior therapy of DM, sex, age, cardiovascular risk group, therapy type (monotherapy or combined therapy), baseline BMI, initial glycemic control.

In addition, change from baseline in HbA1c level will be assessed and evaluated using mixed model repeated measures (MMRM) methodology. The multiple visits for each patient will be incorporated as repeated measures within each patient. Visit will be treated as a categorical predictor and baseline HbA1c level will be included as a covariate. An appropriate covariance structure will be selected to provide estimates (Least Square Means) of change from Baseline and to perform statistical analysis at Visit 3. If the unstructured covariance matrix results in a lack of convergence, the heterogeneous Toeplitz covariance structure, followed by the heterogeneous autoregressive covariance structure, followed by compound symmetry will be used. The dose-response trend hypothesis test will be conducted using the appropriate contrast statement for a linear (ordinal dose) trend. In addition, Least Squares Means, the associated standard errors and 95% confidence intervals will be displayed by each individual dose group.

[figure not shown]
- Proportion (%) of patients with diabetes mellitus type 2 whose HbA1c<7.0% will be described and presented in summary tables using absolute frequencies and percentages as well as 95% confidence intervals;

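### The sizing, the MMRM and the regression have no site term, and no planned interval is adjusted for site; if outcomes correlate within site, the 95% intervals for means and proportions will under-cover

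*SAP*

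**What the plan says.** Protocol 3.1 describes patients "treated with alogliptin or alogliptin FDCs in approximately 40 sites". Protocol 3.1.2 requires consecutive enrolment at each site, and Section 5 leaves treatment to the physician. HbA1c comes from routine tests (Protocol 6.1.4.1 and 6.5), and the site document list in Protocol 9.3 includes "Laboratory certifications and normal ranges for any local laboratories used by the site".

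The sample size is a precision calculation for one paired mean: "power for Confidence Interval for Paired Mean Difference as for accuracy of parameter estimation" (SAP 6, as in Protocol 7.5). Its settings include "Nominal Prob(Width) 0.9" and "Correlation 0.35". That correlation is between the two measurements in a patient, not between patients at a site. At half-width 0.05 the result is: "if Std Dev is 0.65, the required number of pairs is 899".

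In SAP 8.4.2 the MMRM is described thus: "The multiple visits for each patient will be incorporated as repeated measures within each patient". The multiple linear regression lists seven patient-level predictors and no site term. 95% intervals are planned for least squares means, responder proportions and persistence (SAP 8.4.2) and for adverse events (SAP 8.5.2). No interval method is named for the proportions or the adverse events. The primary analysis (SAP 8.4.1) is descriptive and lists no interval, although SAP 6 and 9.2 presuppose one.

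In the readable text, centre enters the analysis only descriptively, in the Protocol Abstract: "Overall and center-specific proportion of participants remaining on alogliptin". Region or country is an optional subgroup covariate. The exploratory analysis text is redacted.

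**The concern.** Patients at one site share physicians, prescribing habits, add-on choices and case mix, so their HbA1c changes may be more alike than those of patients at different sites. If so, the sample carries less information than its head count suggests, and an interval that ignores site is too short for its nominal level.

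This matters because the study has no hypothesis and no formal testing. Interval precision is its only quantitative justification, and Protocol 3.1.1 intends the results to inform prescribers generally, beyond the participating sites.

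Site practice and case mix are the main reasons to expect correlation. Laboratory differences are secondary. A constant laboratory offset cancels in a change from baseline if the same laboratory is used both times. It does not cancel for the HbA1c <7.0% endpoint.

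**Working it through.** **1. Reproducing the plan's figure.** Inputs from SAP 6: per-visit SD 0.65, within-patient correlation 0.35, two-sided alpha 0.05, half-width 0.05, conditional probability 0.90, dropout 25%.

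- SD of change = 0.65 × √(2 × (1 − 0.35)) = 0.741.
- The smallest n for which t × s/√n ≤ 0.05 with conditional probability at least 0.90 is 899.
- 899/(1 − 0.25) = 1198.7, rounded up to 1199.

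All 18 table rows reproduce under independent patients, so the calculation contains no hidden allowance for site.

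**2. Effect of site correlation on a mean or proportion.** The number of sites (40) is from Protocol 3.1. The ICC is an assumption, and equal site sizes are assumed.

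- Patients per site: m = 899/40 = 22.475.
- Design effect: DE = 1 + (m − 1) × ICC.
- Coverage of an unadjusted 95% interval: 2Φ(1.96/√DE) − 1.
- Half-width needed for true 95% coverage, scaled from the 0.05 target: 0.05 × √DE.

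| Assumed ICC | DE | Unadjusted coverage | Half-width if adjusted | Effective N (899/DE) |
|---|---|---|---|---|
| 0 | 1.00 | 95% | 0.050 | 899 |
| 0.01 | 1.21 | 92.5% | 0.055 | 740 |
| 0.02 | 1.43 | 89.9% | 0.060 | 629 |
| 0.05 | 2.07 | 82.7% | 0.072 | 434 |

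The coverage and half-width columns are alternatives. An unadjusted interval stays near its planned width but under-covers; an adjusted one covers properly but is wider. With 40 sites, effective N cannot exceed 40/ICC. At ICC 0.05 that is 800, so no enrolment would reach the planned precision.

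Unequal sites make this worse. With an assumed coefficient of variation of site size of 0.6 and ICC 0.05, DE = 1 + (1.36 × 22.475 − 1) × 0.05 = 2.48, and coverage is about 79%.

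**3. After early termination.** SAP 9.1 says enrolment was far below plan but gives no number, so patients per site is also an assumption. With 5 per site (200 patients in 40 sites):

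| Assumed ICC | DE = 1 + 4 × ICC | Unadjusted coverage |
|---|---|---|
| 0.01 | 1.04 | 94.5% |
| 0.02 | 1.08 | 94.1% |
| 0.05 | 1.20 | 92.6% |

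With an assumed 10 per site and ICC 0.05, DE = 1.45 and coverage is 89.6%.

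**4. Regression.** This design effect applies to means and proportions. Predictors such as sex, age and BMI can vary mostly within site. For such coefficients, omitting a site intercept can make the standard error too large as well as too small.

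**The case against.** The strongest reply is that the study is descriptive and no decision turns on an interval bound. The planned-size figures describe a study that did not happen: SAP 9.1 already concedes that the 0.05 half-width is out of reach, and 9.2 that intervals will be wider. With few patients per site, the loss may be only a point or two of coverage. The size of the loss at the final enrolment is therefore unknown and may be small. However, the wider intervals anticipated in SAP 9.2 reflect a smaller n, not site correlation, so that section does not answer the point.

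A reader might infer that every interval in the plan is too narrow. The documents do not support that. They give no ICC, and at ICC zero nothing is lost. The primary analysis lists no interval at all. For proportions and adverse events the SAP is silent on method and does not state independence. For regression coefficients the direction is not fixed.

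A reader might also take local laboratories as the main cause. Protocol 9.3 is a generic document list, and constant offsets cancel in the primary endpoint if the laboratory does not change.

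The remedy also needs care. Uncorrected cluster-robust standard errors are biased downward when clusters are few, the number of active sites is not given, and a random site intercept adds convergence burden to an MMRM that already has a covariance fallback sequence.

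**Conclusion.** The point holds conditionally. In the readable text, site is absent from the sizing, the MMRM and the regression, and the planned intervals for proportions and adverse events carry no site adjustment. For any positive site ICC, and for inference beyond these sites, unadjusted intervals for means and proportions under-cover.

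The direction is certain under that condition; the size is not. For an assumed ICC of 0.01 to 0.05, coverage runs from 92.5% down to 82.7% at planned size, and from 94.5% down to 92.6% at an assumed 5 per site. The second range is nearer to the study as terminated, but the documents do not give the numbers needed to confirm it. This is an inexpensive improvement worth making before the analysis, not a flaw that invalidates the study.

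**What to change.** - **Models (SAP 8.4.2):** add a random site intercept to the MMRM and the multiple regression. State the fallback if it does not converge, and where it sits relative to the existing covariance sequence.
- **Primary analysis (SAP 8.4.1):** specify a 95% interval for the mean change at Visit 3, using site-clustered variance with a small-sample correction.
- **Proportions (SAP 8.4.2):** name the interval method for the responder and persistence proportions, and use the same site-clustered variance with correction.
- **SAP 6 and 9:** state that the half-width figures assume no site clustering. Give the numbers of active sites and patients per site, so that a reader can judge the effect.

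No new data are needed, since patients are enrolled and logged by site. The costs are some programming, a possible convergence problem, and somewhat wider intervals for means and proportions. If the site ICC is near zero, the results should barely change.
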